The double-blind treatment period of the study includes a baseline visit (of up to 15 days; extensions to the 15-day baseline visit period [e.g., to complete [¹⁸F]GTP1 PET imaging] may be granted on a case-by-case basis by the Medical Monitor), a 68-week treatment period (Weeks 1–69), and an efficacy assessment period (baseline to Week 73). Treatment with study drug will occur Q2W for the first three doses (i.e., doses at Weeks 1, 3, and 5) and Q4W thereafter, up to and including the Week 69 dose (for a total of 19 doses). There will be no administration of study drug at the Week 73 visit. Safety, efficacy, PK, and biomarker assessments will be performed at baseline (during screening, the baseline visit, or at the Week 1 visit, prior to initiation of study drug) and at several postbaseline visits, including the Week 73 visit. See [Appendix 1](#) for details regarding study activities during the double-blind treatment period.

Open-Label Extension Period

[figure not shown]
An optional 96-week OLE period is available to patients who complete the double-blind treatment period and who, in the judgment of the investigator, would potentially benefit from open-label MTAU9937A treatment. For the OLE period, all patients will receive MTAU9937A 4500 mg IV. Safety and efficacy assessments during the OLE period will

be performed at a schedule similar to that of the double-blind treatment period. The procedure(s) performed for tau-based biomarker evaluation during the OLE period ($[^{18}\text{F}]\text{GTP1}$ PET imaging and/or LP) should match the procedure(s) performed during the double-blind treatment period; LP will remain optional, but encouraged, for any patient who continues with longitudinal $[^{18}\text{F}]\text{GTP1}$ PET imaging and had a screening or baseline LP. See [Appendix 2](#) for details regarding study activities during the OLE period.

Safety Follow-Up Period

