4.3.2.1 MTAU9937A and Placebo

MTAU9937A will be prepared and diluted into 100-mL IV bags according to the pharmacy manual, and infusions will be administered per the instructions outlined in [Table 2](#) and the pharmacy manual.

Table 2 Administration of First and Subsequent Infusions of MTAU9937A

First Infusion	Subsequent Infusions

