
 • Begin infusion at an initial rate of 0.5 mL/min (30 mL/hr). • If no infusion-related or hypersensitivity reaction occurs during the first 30 minutes, then increase the rate to 1.0 mL/min (60 mL/hr). • If no infusion-related or hypersensitivity reaction occurs during the subsequent 30 minutes, then increase the rate to 3.0 mL/min (180 mL/hr) • If a reaction develops, stop or slow the infusion. Administer medications and supportive care in accordance with institutional guidelines. The patient should be monitored until all infusion-related adverse events are Grade 1 or are resolved. 
If the reaction resolves, resume the infusion at a 50% reduction in rate (i.e., 50% of rate being used at the time that the reaction occurred). If the reaction recurs after resumption of the infusion, then stop the infusion. For patients who experience serious or severe hypersensitivity or hypersensitivity-like reactions (e.g., hypotension, mucosal involvement), the investigator must discuss with the Medical Monitor whether to continue study drug treatment.
	
 • If the participant experienced an infusion-related or hypersensitivity reaction during the prior infusion, begin infusion at an initial rate of 0.5 mL/min and follow instructions for first infusion. • If the participant tolerated the prior infusion well (defined by an absence of Grade 2 reactions during a final infusion rate of 3.0 mL/min), begin infusion at a rate of 3.0 mL/min. • If a reaction develops, stop or slow the infusion. Administer medications and supportive care in accordance with institutional guidelines. The patient should be monitored until all infusion-related adverse events are Grade 1 or are resolved. 
If the reaction resolves, resume the infusion at a 50% reduction in rate (i.e., 50% of rate being used at the time that the reaction occurred). If the reaction recurs after resumption of the infusion, then stop the infusion. For patients who experience serious or severe hypersensitivity or hypersensitivity-like reactions (e.g., hypotension, mucosal involvement), the investigator must discuss with the Medical Monitor whether to continue study drug treatment.

4.3.2.2 [18F]GTP1 Tau PET Radioligand

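### Table 2 would start former placebo patients' first active infusion (Week 77) at 3.0 rather than 0.5 mL/min, unless the pharmacy manual says otherwise

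*Protocol*

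**What the plan says.** Protocol Section 4.3.2.1 covers both MTAU9937A and placebo. It relies on two sources for how infusions are run, Table 2 and the pharmacy manual, and names them in the sentence that begins "MTAU9937A will be prepared and diluted into 100-mL IV bags according to the pharmacy manual, and infusions will be administered per the instructions outlined in". The table is titled "Administration of First and Subsequent Infusions of MTAU9937A" and has two columns.

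- **First infusion.** "Begin infusion at an initial rate of 0.5 mL/min (30 mL/hr"). The first step up is conditional: "If no infusion-related or hypersensitivity reaction occurs during the first 30 minutes, then increase the rate to 1.0 mL/min (60 mL/hr"). After a further 30 minutes without a reaction the rate rises to 3.0 mL/min.
- **Subsequent infusions.** After a reaction the slow start applies: "If the participant experienced an infusion-related or hypersensitivity reaction during the prior infusion, begin infusion at an initial rate of 0.5 mL/min". Otherwise the condition is "If the participant tolerated the prior infusion well (defined by an absence of Grade 2 reactions during a final infusion rate of 3.0 mL/min"), and the infusion then begins at 3.0 mL/min.

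Section 3.1.1.1 fixes the calendar. The last double-blind dose is at Week 69, and "There will be no administration of study drug at the Week 73 visit". Appendix 2 shows dosing resuming at Week 77. On the extension, Section 3.1.1.1 states: "For the OLE period, all patients will receive MTAU9937A 4500 mg IV".

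SAP Section 2.3 keeps patients, investigators and site monitors blinded until all patients have finished blinded follow-up or moved into the extension. Protocol Section 4.2 makes an exception for the site pharmacist and one CRO monitor.

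**The concern.** The rule for later infusions assumes that tolerance of the last infusion predicts tolerance of the next. That assumption fails at Week 77 for patients randomised to placebo: tolerating placebo at Week 69 is no evidence about tolerating the antibody. Yet Table 2 turns only on the prior infusion, so a site following it literally would give these patients their first active dose at the full rate.

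What is at stake is patient safety at one visit. Section 5.1.1.1 names hypersensitivity, including severe anaphylactic reactions, as a potential risk of the antibody. The stepwise start is the protocol's own means of limiting exposure before a reaction shows itself. It would be lost by omission, not by a stated decision. The Week 73 efficacy analysis and the randomised safety comparison are not touched.

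**Working it through.** The plan gives no figure of its own on this point, so the check is a reading of the rules followed by simple arithmetic.

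**Calendar.** Three doses at Weeks 1, 3 and 5, then every 4 weeks to Week 69: 3 + (69 − 5)/4 = 19 doses, which matches Section 3.1.1.1. With no dose at Week 73, the infusion before Week 77 is normally Week 69, 8 weeks earlier.

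**Which column applies at Week 77?** The places that could answer this are silent:

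| Place in the protocol | Week 77 infusion rate |
|---|---|
| Section 3.1.1.1, open-label extension | none |
| Section 4.3.2.1 and Table 2 | none; refers only to the prior infusion |
| Section 5.1.1.1, hypersensitivity risk | none |
| Section 5.1.3.2, reaction management | none |
| Appendix 2, schedule and footnotes | none |

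Appendix 2 footnote s repeats at Week 77 the serum PK timings of Week 1 (Appendix 1 footnote aa), but nothing repeats the Week 1 infusion ramp.

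**Size of the rate difference.** The opening-rate ratio is 3.0/0.5 = 6 at any volume. In the first 30 minutes, 0.5 × 30 = 15 mL runs under the first-infusion column against 3.0 × 30 = 90 mL under the other, provided the total volume is at least 90 mL. Total volume is not stated; Section 4.3.2.1 mentions only 100-mL bags. If 4500 mg were in 100 mL (an assumption), the concentration would be 45 mg/mL and the opening rates 22.5 and 135 mg/min.

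**Patients who could be affected.** SAP Section 2.2 gives 137 randomised to placebo, which agrees with 457 × 3/10 = 137.1. The same section assumes 25% dropout. Extension uptake is not given, so it is shown as a range:

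| Assumed uptake among completers | Former placebo patients |
|---|---|
| 100% | 137.1 × 0.75 = 102.8 |
| 75% | 102.8 × 0.75 = 77.1 |
| 50% | 102.8 × 0.50 = 51.4 |

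These are upper figures. Patients with a reaction at Week 69 restart at 0.5 mL/min anyway. Section 4.1.2 allows earlier MTAU9937A in the Phase I study, so a few may have had the antibody before. Patients already past Week 77 are beyond reach of a change.

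**Time added by using the first-infusion column.** For volume V ≥ 45 mL:

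- First-infusion column: 30 min (15 mL) + 30 min (30 mL) + (V − 45)/3 min = 60 + (V − 45)/3.
- Subsequent column: V/3 min.
- Difference: 60 − 45/3 = 45 min, whatever V is. At V = 100 mL this is 78.3 against 33.3 min.

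**The case against.** Five points can be made in the plan's defence.

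- **The pharmacy manual also governs infusions and may hold a Week 77 rule.** This stands as a condition on the finding. What is shown is that the protocol is silent, not that the trial has no such rule.
- **The title of Table 2 refers to infusions of MTAU9937A, so Week 77 is literally a former placebo patient's first.** The reading is available. But the section covers placebo as well, and blinded staff cannot tell who these patients are. It works for them only if everyone is slowed, which the protocol never says. A site could choose that or ask the Medical Monitor, but nothing directs it to.
- **The site pharmacist is unblinded.** True, but the protocol gives that role no rate instruction, and slowing only former placebo patients would reveal their arm.
- **The repeated PK sampling proves little.** Fair. The 1500 mg and 8100 mg arms also change dose at Week 77, which explains the sampling equally well. The finding does not need this comparison.
- **No harm is shown.** Also fair. Section 1.2.2 reports that the drug was generally well tolerated, with no adverse drug reactions identified and Phase I doses well above 4500 mg, though it gives no infusion rates. Section 5.1.1.3 reports no treatment-emergent anti-drug antibodies in Phase I. Rules for stopping or slowing, monitoring during and just after infusion, reaction management, vital signs 60–90 minutes afterwards and the Appendix 5 precautions all remain. They act mainly once a reaction has begun; the ramp limits exposure beforehand.

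**Conclusion.** The concern holds. Followed as written, Table 2 starts the first active infusion of former placebo patients who tolerated Week 69 at 3.0 mL/min, six times the rate that the protocol sets for a first infusion. This affects at most 137 patients, and about 51 to 103 at 25% dropout with 50% to 100% uptake, less those with a Week 69 reaction or already past Week 77.

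The conclusion rests on two conditions: that the pharmacy manual contains no Week 77 rule, and that blinded sites apply Table 2 uniformly. It is not a claim that 3.0 mL/min is unsafe. It is a worthwhile, inexpensive safety correction, held with moderate confidence because the manual was not available.

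**What to change.** Check the pharmacy manual first. If it already requires the slow start for everyone at Week 77, a cross-reference in Table 2 is enough. If not, add to Table 2 and Appendix 2: *At Week 77, use the First Infusion column for all patients*, and put a matching line in the manual. One rule for everyone can be applied by a blinded site and does not disclose the arm.

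The cost is 45 minutes of infusion once per extension patient, at a visit that already requires PK sampling to 4 hours after the infusion. At 25% dropout and full uptake, 457 × 0.75 = 342.75 patients × 45 min = 257 infusion-hours, or 257.1/97 = 2.65 hours per site; at 50% uptake the total is about 129 hours. Most of this falls on patients already receiving active drug (457 × 0.7 × 0.75 = 240), who do not need the ramp as a first exposure. That is the price of keeping the blind. The amendment also needs ethics committee and regulatory approval as locally required (Section 9.6).

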4.3.2.3 Amyloid PET Radioligands

All patients enrolled using amyloid PET evaluation will be assessed by PET imaging using an appropriate amyloid PET radioligand. Refer to the Amyloid Imaging Technical Operations Manual for details on the use of the amyloid PET radioligands.

4.3.3 Investigational Medicinal Product Accountability

IMPs required for completion of this study (MTAU9937A or placebo) and radiotracers (which may be IMPs or NIMPs) will be provided by the Sponsor where required by local health authority regulations. The study site will acknowledge receipt of IMPs, using the

appropriate documentation mechanism (system or paper form), to confirm the shipment condition and content. Any damaged shipments will be replaced.

IMPs will either be disposed of at the study site according to the study site's institutional standard operating procedure or will be returned to the Sponsor with the appropriate documentation. The site's method of MTAU9937A/placebo destruction must be agreed to by the Sponsor. The site must obtain written authorization from the Sponsor before any MTAU9937A/placebo is destroyed, and MTAU9937A/placebo destruction must be documented on the appropriate form. Radioligands will be disposed of or returned according to instructions provided by the PET imaging vendor.

Accurate records of all study treatments (received at, dispensed from, returned to, and disposed of by the study site should be recorded on the applicable Drug Inventory or Dispensing Logs.

4.3.4 Continued Access to MTAU9937A

Currently, the Sponsor (Genentech, a member of the Roche Group) does not have any plans to provide Sponsor study drug (MTAU9937A) or any other study treatments or interventions to patients who have completed the study. The Sponsor may evaluate whether to continue providing MTAU9937A in accordance with the Roche Global Policy on Continued Access to Investigational Medicinal Product, available at the following Web site:

http://www.roche.com/policy_continued_access_to_investigational_medicines.pdf

4.4 CONCOMITANT THERAPY

Concomitant therapy consists of any medication (e.g., prescription drugs, over-the-counter drugs, vaccines, herbal or homeopathic remedies, nutritional supplements) used by a patient in addition to protocol-mandated treatment from *3 months* prior to *the start of* screening until the final study visit. However, any agent that targets A β used by the patient at any time during their life is also considered to be a concomitant therapy. All such medications should be reported to the investigator and recorded on the appropriate Concomitant Medications eCRF.

4.4.1 Permitted Therapy

All participants who use concomitant therapies should continue to use those therapies, unless they conflict with the inclusion or exclusion criteria as stated in Sections [4.1.1](#) and [4.1.2](#).

Non-investigational therapies for AD are permissible, provided that the dosing regimen has been stable for 2 months prior to screening. At the time of enrollment, there should be no a priori intent to initiate, discontinue, or alter the dose of any AD therapy for the duration of the study. However, following the initiation of study drug, standard-of-care symptomatic medications for AD may be initiated, dose adjusted, or discontinued as deemed clinically appropriate.

4.4.2 Cautionary Therapy

4.4.2.1 Herbal Therapies

Concomitant use of herbal therapies is not recommended because their pharmacokinetics, safety profiles, and potential drug-drug interactions are generally unknown. However, herbal therapies may be used during the study at the discretion of the investigator.

4.4.3 Prohibited Therapy

Refer to the exclusion criteria (Section 4.1.2) for a list of prohibited therapies and exceptions.

4.5 STUDY ASSESSMENTS

The schedule of activities to be performed during the study is provided in [Appendix 1](#) and [Appendix 2](#). All activities must be performed and documented for each patient.

Patients will be closely monitored for safety and tolerability throughout the study. Patients should be assessed for toxicity prior to each dose; dosing will occur only if the clinical assessment and *available* local laboratory test values are acceptable.

4.5.1 Informed Consent Forms and Screening Log

Written informed consent for participation in the study must be obtained before performing any study-related procedures (including screening evaluations). Informed Consent Forms for enrolled patients and for patients who are not subsequently enrolled will be maintained at the study site.

All screening evaluations must be completed and reviewed to confirm that patients meet all eligibility criteria before enrollment. The investigator will maintain a screening log to record details of all patients screened and to confirm eligibility or record reasons for screening failure, as applicable.

4.5.2 Medical History, Concomitant Medication, and Demographic Data

Medical history, including clinically significant diseases, surgeries, cancer history (including prior cancer therapies and procedures); reproductive status; smoking history; and use of alcohol and drugs of abuse; and recent history (5 years) of non-elective hospitalizations, pneumonia or cardiovascular events, will be recorded at baseline.

In addition, all medications (e.g., prescription drugs, over-the-counter drugs, vaccines, herbal or homeopathic remedies, nutritional supplements) used by the patient within *3 months* prior to initiation of screening until the final study visit will be recorded. Any agent that targets A β used by the patient at any time during their life (any time before initiation of screening and while on study) will also be recorded. At the time of each follow-up physical examination, an interval medical history should be obtained and any changes in medications and allergies should be recorded.

Demographic data will include age, sex, self-reported race/ethnicity, and years of education. Demographic data will be collected for both the patient and the caregiver.

As this study is being conducted in multiple geographic regions, it is likely that patients of different ethnic origins will be enrolled in the study. Although there is currently no indication that MTAU9937A is metabolized or eliminated differently or that the treatment effect would be different in patients with different ethnic origins, collecting this information (where permitted by local regulations) is essential to adequately evaluate the results of this study (e.g., possible differences in PK exposure [concentration of the drug in the blood] or treatment effect).

4.5.3 Physical Examinations

A complete physical examination, performed at screening and other specified visits, should include an evaluation of the head, eyes, ears, nose, and throat, and the cardiovascular, dermatological, respiratory, and gastrointestinal systems. In addition, the musculoskeletal and genitourinary systems should be examined as clinically indicated. Any abnormality identified at baseline should be recorded on the General Medical History and Baseline Conditions eCRF.

Limited, symptom-directed physical examinations should be performed at specified postbaseline visits and as clinically indicated. Changes from baseline abnormalities should be recorded in patient notes. New or worsened clinically significant abnormalities should be recorded as adverse events on the Adverse Event eCRF.

4.5.4 Neurological Examinations

A complete neurologic examination should include the evaluation of consciousness, cranial nerves, motor and sensory system, coordination and gait, and reflexes. Changes from baseline abnormalities should be recorded at each subsequent neurologic examination. New or worsened abnormalities should be recorded as adverse events on the Adverse Event eCRF if considered clinically significant in the investigator's judgment.

4.5.5 Lumbar Puncture

For patients consenting to LP, the LP procedure should be performed according to standard procedures at the study site using sterile technique and an atraumatic needle. See the laboratory manual for details regarding the collection, processing, and storage of CSF.

4.5.6 Vital Signs

Vital signs will include measurements of respiratory rate, pulse rate, and systolic and diastolic blood pressure while the patient is in a seated position, and temperature.

The same arm should be used for all blood pressure measurements. Pulse rate and blood pressure should not be measured unless 15 minutes have passed since the last blood draw. Vital sign assessments should be performed just prior to study drug administration.

4.5.7 Clinical Outcome Assessments

The COAs listed in [Table 3](#) will be administered to all patients and/or caregivers enrolled in this study. Clinicians/raters (but not caregivers or patients) will use an electronic device to capture COA data. COA data from the electronic device will be transmitted to a centralized database maintained by the electronic device vendor. The C-SSRS will be used to monitor safety (as described below). All other COAs will only be used as assessments of treatment efficacy.

Table 3 Clinical Outcome Assessments

Clinical Outcome Assessments	Concept
Mini-Mental State Examination (MMSE)	Cognition
Clinical Dementia Rating Scale (CDR)	Cognition and Function
Repeatable Battery for the Assessment of Neuropsychological Status (RBANS)	Cognition
Alzheimer’s Disease Assessment Scale–Cognitive Subscale (ADAS-Cog 13)	Cognition
Amsterdam Instrumental Activity of Daily Living Questionnaire (iADL)	Function
Alzheimer’s Disease Cooperative Study Group–Activities of Daily Living Inventory (ADCS-ADL)	Function
Alzheimer’s Disease Event Inventory (ADEI)	Significant events
Resource Utilization in Dementia–Lite (RUD-lite)	Resource utilization
Columbia-Suicide Severity Rating Scale (C-SSRS)	Suicidality
Diagnostic Classification	Diagnosis
Caregiver Global Impression of Change Scales for Alzheimer’s disease (CaGI-Alz)	Cognition and Function

The questionnaires, translated into the local language as required, will be completed in their entirety at specified timepoints during the study. To ensure instrument validity and that data standards meet health authority requirements, questionnaires will be administered before the patient, clinician, or caregiver receives any information regarding disease status, prior to the performance of non-COA assessments and administration of study drug or radioligand, unless otherwise specified.

The COA scales and assessments for this study will be provided unless otherwise specified. Whenever possible, there should be consistency in the rater and caregiver

who complete the scales for each patient throughout the duration of the study. Potential raters should be designated at each site and will receive training and be approved by the rating-scale vendor prior to being allowed to administer any cognitive assessments/rating scales in the study. Administration of cognitive assessments/rating scales (i.e., the COAs) will be done in accordance with instructions provided in the GN39763 COA Manual and the training/documentation provided by the rating-scale vendor.

In addition, given that the primary outcome measure in this study involves subjective judgment, the adequacy of patient interviews and ratings will be monitored by an endpoint reliability program administered by the rating-scale vendor; this is considered to be an essential part of good research methodology. Prior studies have clearly demonstrated that the failure to adequately monitor such ratings can substantially increase the risks of failed trials (Becker and Greig 2008; Kobak 2010).

Please see the GN39763 COA Manual for instructions on COA administration order, specification of list versions to use at each visit, rater roles, restrictions on raters, and additional details on COA administration and the endpoint reliability program.

